To study sugar-sweetened beverages, we will conduct a survey asking consumers to make incentivized purchasing decisions for sugar-sweetened beverages. We will have three treatment arms showing subjects one of the following: (i) the nutrition label for the beverages, (ii) a warning label with text stating that consuming sugar-sweetened beverages can have adverse health consequences, and (iii) graphic warning label that shows images associated with diabetes, obesity, and tooth decay. We will also ask consumers to answer a series of nutrition knowledge questions, so that we can measure how the change in consumption behavior from an NPI correlates with their (lack of) nutritional knowledge.

2. Background

PROTOCOL
Soc-Behav-Ed Exempt
Berkeley

Protocol # 2020-08-13558
Date Printed: 08/17/2021

Protocol Title: Optimal non-financial policy instruments: fuel-efficient cars and sugar-sweetened beverages
Protocol Type: Soc-Behav-Ed Exempt
Date Submitted: 06/27/2021
Important Note: This Print View may not reflect all comments and contingencies for approval. Please check the comments section of the online protocol. Questions that appear to not have been answered may not have been required for this submission. Please see the system application for more details.

a) Give relevant background (e.g., summarize previous/current related studies) on condition, procedure, product, etc. under investigation, including citations (with attached bibliography) if applicable.

Our project is related to several existing literatures. First, there are several studies which seek to quantify the effects of specific NPIs on purchasing behavior and wellbeing. One example is [name] and Kessler (2019), which uses a field experiment to study the impact of home energy social comparison reports on consumer wellbeing. We will contribute by creating a comprehensive theoretical framework to understand whether an NPI is normatively good or bad. Using our online surveys, we will outline how to measure the relevant empirical parameters in practical settings. Second, we relate to a public health literature studying the effects of graphic warning labels on consumption for sugar-sweetened beverages, including Donnelly et al. (2018) and Grummon et al. (2019).

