- Participants will be told they are shopping for sugar-sweetened beverages and asked to enter their name and the address where they want the product shipped.
- Participants will then be shown a picture of one of these sugar-sweetened beverages and a similar sugar free beverage (e.g., Minute Maid Lemonade and LaCroix Lemon). They will then answer a series of questions about whether they would prefer to buy the sugar-sweetened beverage for \$X or the sugar-free beverage for \$Y. Participants will answer these questions for three pairs of beverages, and are told they have a 1/3 chance of actually receiving beverages per one of their decisions.
- Participants will then be shown three more pairs of beverages with additional information displayed on the screen (the "treatment"). All information provided will be true and factual. They will randomly be shown one of the following: (i) nothing (the control group), (ii) the nutrition labels for each beverage, (iii) a graphic warning label, or (iv) a warning label with text outlining negative health consequences of drinking beverages with added sugar.
- Total participation time is approximately 10-20 minutes to complete both parts of the survey. All questions for both parts of the survey are attached (attachment_survey(ssb_part1 and attachment_survey(ssb_part2).

• Participants will be paid \$6 for completing this survey: \$2 for completing part I and \$4 for completing part II.

• Additionally, all participants will receive an additional \$7.00 budget. For these participants, we will randomly choose one of the purchase decisions, and they will receive their choice of beverage (either the sugar-sweetened beverage or the sugar-free beverage) and \$7.00 minus the price of the drink. For example, if on the randomly chosen question, participants say they prefer Minute Maid Lemonade for \$4.50 to LaCroix Lemon for \$3.00, then they will receive the Minute Maid Lemonade and an additional \$2.50.

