*** Subject Population ***

5. Subject Population

Describe proposed subject population, including criteria for study inclusion and exclusion (e.g., age, health status, language, gender, race, ethnicity). State the maximum number of subjects planned for the study. This number should account for all subjects to be recruited, including those who may drop out or be found ineligible.

For the sugar-sweetened beverages survey, our study population consists of participants recruited via Facebook ads who are shopping for soda. We aim to recruit a sample that will be broadly representative of the U.S. population in terms of race, gender, and education. We plan to overrecruit adults aged 65 or older so that they comprise approximately 25% of our sample. All U.S. residents aged 18 years or older will be eligible to enroll in our experiment.

For the fuel cost survey, our study population consists of AmeriSpeak panelists who own or are leasing a car. The survey will be advertised to AmeriSpeak panelists using a generic title (to avoid biasing respondents), as is common on these surveys: "Answer a 10-20 minute decision choice survey. You must own or be leasing a car to take this survey." All panelists are at least 18 years old. In addition, AmeriSpeak will work to ensure our subject population is nationally-representative along key demographics (race, gender, age, income, and education).

The maximum number of subjects planned for the study is 2,000 workers for the fuel cost survey and 3,000 workers for the sugar-sweetened beverages survey.

PROTOCOL
Soc-Behav-Ed Exempt
Berkeley

Protocol # 2020-08-13558
Date Printed: 08/17/2021

Protocol Title: Optimal non-financial policy instruments: fuel-efficient cars and sugar-sweetened beverages

Protocol Type: Soc-Behav-Ed Exempt

Date Submitted: 06/27/2021

Important Note: This Print View may not reflect all comments and contingencies for approval. Please check the comments section of the online protocol. Questions that appear to not have been answered may not have been required for this submission. Please see the system application for more details.

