Are Sugar-Sweetened Beverage Information Labels Well-Targeted?

NCT05038163

Statistical Analysis Plan

April 1, 2021

Are Sugar-Sweetened Beverage Information Labels Well-Targeted? Evidence and Welfare Implications

Sample Size and Power

The goal of this experiment is not to accept or reject a particular hypothesis, but rather to measure the targeting properties and welfare effects of information labels with statistical precision. Thus, our power calculations are based on 95%-confidence intervals.

We use related preliminary work to estimate our standard errors for this project; a summary of this early work is available at the end of this document. In our preliminary work, each label was assessed with approximately 180 participants, with 90 assigned to a control arm and to each of two labels, and the 95%-confidence intervals for the treatment effects have width of about \$0.50 per item, or roughly 25% of the average estimated bias. For our proposed project, a sample size of approximately 3,000 subjects will give us a total sample of 1,000 to assess each label (i.e., 500 from the control and 500 from the treatment group). Assuming the same variances as in our preliminary work, this will give us standard errors that are $\sqrt{1000/180} \approx 2.4$ times smaller than in our preliminary work. Our 95%-confidence intervals for our treatment effects will have width of approximately \$0.21 per item, or roughly 10% of the average estimated bias. Under the same assumptions, our 95%-confidence intervals for our targeting measure (i.e., the covariance) will be approximately 2.4 times smaller than in our preliminary work and have width of approximately 0.26 dollars squared.

For the subsample of older adults, we will have approximately 250 participants to assess each label (i.e., 125 from the control and 125 from the treatment group). If we assume the variances on the treatment effects and measure of targeting are the same as for the full sample, then we can again predict power. Under this assumption, we will have standard errors that are $\sqrt{250/180} \approx 1.4$ times smaller than in our preliminary work. Our 95%-confidence intervals for our treatment effects will have width of approximately \$0.36 per item, or roughly 20% of the average estimated bias for the full population. Similarly, our 95%-confidence intervals for our targeting measure (i.e., the covariance) will have width of approximately 0.45 dollars squared.

Statistical Design

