To ensure that our statistical methods are sufficiently well-powered, we have already piloted the soft drinks experiment with 270 Amazon Mechanical Turk (MTurk) participants making hypothetical choices. As shown in the top left panel of Figure A.8 below, we estimate that on average, consumers underweight the health costs of sugary drinks by about $\$2$ per 12-pack of 12-oz drinks. The labels have an average treatment effect (ATE) of decreasing WTP for the sugary drinks by about $\$0.50$. In an aggregate sense, these effects look like they are "in

the right direction," partially counteracting consumer bias. Unfortunately, as the top right panel shows, while the treatment effects of these labels are heterogeneous (the variance is significant and positive), they are not targeted to the consumers making the biggest mistakes (the covariance is approximately zero).

When these statistics are combined with our theoretical formula (assuming a pass-through parameter of $\rho = 1$ for simplicity), the bottom panel shows that in the absence of any taxes and subsidies, the labels do increase welfare by about \$0.50 per pack, as on aggregate they reduce over-consumption of the drinks. However, the bottom panel also shows that at the optimal sugary drinks tax, these labels in fact decrease social welfare. This is because the average decrease in consumption generated by the labels is no longer beneficial, and thus their highly heterogeneous but poorly targeted effects simply create "noise" in consumer choices. Our preliminary finding of differential benefits of the labels in the presence and absence of a sugary drinks tax illustrates how the combination of our theoretical formula and measurement techniques can be used to quantify the nuanced economic effects of these instruments.

Figure A.8: Results from hypothetical choice pilot

Note: Estimates are calculated from a hypothetical choice pilot of 270 participants on MTurk.

We plan to keep using hypothetical choice pilots to test new labels, and plan to have a set of five labels in the incentivized choice experiment.

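### The SAP's per-arm counts and full-sample interval widths fit six arms, but the protocol randomises to four, and the SAP makes no allowance for loss before Part II

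*SAP*

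**What the plan says.** The SAP justifies its sample size by interval width and not by a test: "Thus, our power calculations are based on 95%-confidence intervals". Its Sample Size and Power section states that "a sample size of approximately 3,000 subjects will give us a total sample of 1,000 to assess each label", made up of 500 control and 500 label participants. From this it derives 95% interval widths of about $0.21 per item for a treatment effect and 0.26 dollars squared for the targeting covariance. For older adults it gives 125 per arm, 250 per label comparison, and widths of $0.36 and 0.45. The inputs come from a pilot in which "each label was assessed with approximately 180 participants, with 90 assigned to a control arm and to each of two labels". Under Related Preliminary Work, the SAP says that the investigators "plan to have a set of five labels in the incentivized choice experiment".

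The protocol describes a different set of arms. Section 1 (Purpose of the study) says: "We will have three treatment arms showing subjects one of the following: (i) the nutrition label for the beverages", followed by a text warning and a graphic warning. Section 4 (Study Procedures, sugar-sweetened beverages survey) lists four randomised conditions, beginning with no label and the nutrition labels and ending with "iii) a graphic warning label, or (iv) a warning label with text". Section 5 (Subject Population) gives a maximum of 3,000 for this survey. The form item being answered asks for a number that covers everyone recruited, "including those who may drop out or be found ineligible".

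**The concern.** The interval widths are the only justification that the SAP offers for the sample size, so they should belong to the design that will be run. As written, the two documents disagree on how many labels are evaluated. Someone who later compares the report with the plan could not tell whether two labels were dropped or were never intended.

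The 3,000 also plays two roles. In the protocol it is the recruitment maximum. In the SAP the whole 3,000 is divided among the arms that produce the estimates. The labels and the price-list outcomes belong to Part II, which is sent 2-3 days after Part I and only to those who completed Part I. Anyone lost between the parts adds nothing to the estimates, yet the SAP makes no allowance for this.

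**Working it through.** **Inputs.** From the SAP: pilot treatment-effect width $0.50 at 180 per comparison; about 3,000 participants; 500 per arm; 125 per arm for older adults; planned covariance width 0.26. From the protocol: four conditions, a maximum of 3,000, and 25% aged 65 or older. Neither document gives a loss rate, so 10-30% is an assumption. The protocol states no allocation ratio, so equal arms are also assumed.

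**Reproducing the full-sample figures.** Width = 0.50 / √(n/180), where n is the number per label comparison (control plus label).
- At n = 1,000, √(1000/180) = 2.357 and 0.50/2.357 = $0.212. The stated $0.21 reproduces.
- The passages cited here do not state a pilot covariance width. Working back from the SAP's own figure, 0.26 × 2.357 = 0.613. The covariance widths below scale from this, so agreement at n = 1,000 is built in and is not an independent check.
- The SAP's covariance formula uses the label arm only, but the scaling is the same because 500/90 = 1000/180.

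**Number of arms implied by the SAP.**
- Full sample: 3,000/500 = 6.
- Older adults: 0.25 × 3,000 = 750, and 750/125 = 6.
- Five labels plus one control = 6.
- A shared control matches the pilot: 3 × 90 = 270, and the pilot is described as having "270 Amazon Mechanical Turk (MTurk) participants making hypothetical choices".

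**Number of arms in the protocol.** One control plus three labels = 4, so 3,000/4 = 750 per arm and n = 1,500 per comparison.

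**Full-sample widths with 3,000 recruited.**

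| Design | Loss | Per arm | n per comparison | Treatment effect | Covariance |
|---|---|---|---|---|---|
| Six arms | 0% | 500 | 1,000 | $0.212 | 0.260 |
| Six arms | 10% | 450 | 900 | $0.224 | 0.274 |
| Six arms | 30% | 350 | 700 | $0.254 | 0.311 |
| Four arms | 0% | 750 | 1,500 | $0.173 | 0.212 |
| Four arms | 10% | 675 | 1,350 | $0.183 | 0.224 |
| Four arms | 30% | 525 | 1,050 | $0.207 | 0.254 |
| Four arms | 33.3% | 500 | 1,000 | $0.212 | 0.260 |

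Break-even for four arms: 4 × 500 = 2,000 analysed, and 1 − 2,000/3,000 = one third lost.

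**Older adults.** The SAP prints √(250/180) as about 1.4. The square root is 1.18, while 250/180 itself is 1.39, so the root appears not to have been taken.
- Six arms, n = 250: 0.50/1.179 = $0.42 and 0.613/1.179 = 0.52, against the stated $0.36 and 0.45.
- Four arms without loss, n = 0.25 × 1,500 = 375: √(375/180) = 1.443, giving $0.35 and 0.42.

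**The case against.** Several objections have weight.

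- **The two effects offset.** Fewer arms narrow the intervals and loss widens them. For the protocol's four arms, every value in the assumed 10-30% range is at or inside the stated full-sample widths. This stands. A reader might infer that the study is too small for its stated precision, but the documents do not support that. The wider values need both five labels, which the protocol does not list, and a loss rate that neither document gives. The SAP also aims at estimation, so no power threshold is missed.
- **Six arms is an inference.** The SAP never states a number of arms. Dividing 3,000 by three labels also gives 1,000 per label, and 750 by three gives 250 older adults. Halving those gives 500/500 and 125/125. But with a shared control, four arms of 500 use only 2,000 people, so that reading would itself contain an error. The five-label sentence and the pilot layout favour six. Under either reading, the protocol's count is 750 per arm without loss.
- **The five-label sentence looks forward, and the dates differ.** It sits under preliminary work. The SAP is dated April 1, 2021, and the protocol's second amendment was approved on 08/17/2021. This may explain the mismatch, but no text resolves it.
- **The words about dropouts belong to the form.** The investigators' answer gives only a maximum of 3,000, and the SAP does not say whether its 3,000 are recruited or analysed. This softens the point on loss, but the absence of any allowance remains.

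**Conclusion.** The documents disagree on the number of labels, and the SAP's per-arm counts and full-sample widths are not those of the protocol's design. For four equal arms without loss, the figures are 750 per arm, about $0.17 and 0.21 dollars squared, in place of 500, $0.21 and 0.26. The stated full-sample widths survive up to about one-third loss, so the fault is an unreconciled design basis and not demonstrated under-precision. Only if five labels are run within 3,000 recruits does the assumed 10-30% loss push the widths beyond those stated, to $0.22-0.25 and 0.27-0.31.

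A reader might also infer that the stated 65+ widths are those of a six-arm design. They are not: the 125-per-arm count fits six arms, but $0.36 and 0.45 do not follow from it, because of the square-root slip.

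These results rest on equal allocation, a shared control, the SAP's assumption of unchanged pilot variances, an assumed loss range and a back-calculated pilot covariance width.

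**What to change.** 1. Settle the number of labels. Either remove the five-label sentence from the SAP or amend the protocol's arm list.
2. For that design, restate the per-arm counts and both full-sample widths using expected Part II completers. State the loss assumption and whether 3,000 means recruited or analysed.
3. Recompute the 65+ widths at the same time, with the square root taken. Before any loss, the replacements are about $0.35 and 0.42 for four arms, or $0.42 and 0.52 for six.

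The cost is SAP wording, or one protocol amendment if five labels are kept. Stating the design consistently needs no added participants.

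### The older-adult precision forecast does not apply its square root: √(250/180) is 1.18, not 1.4, so the interval widths should be about $0.42 and 0.52 dollars squared, not $0.36 and 0.45

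*SAP*

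**What the plan says.** The SAP's Sample Size and Power section rests on the width of 95% confidence intervals and not on a hypothesis test. Its starting point is a pilot in which "each label was assessed with approximately 180 participants, with 90 assigned to a control arm and to each of two labels", and in which "the 95%-confidence intervals for the treatment effects have width of about \$0.50 per item, or roughly 25% of the average estimated bias".

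For the full sample it plans "a total sample of 1,000 to assess each label (i.e., 500 from the control and 500 from the treatment group", takes the standard errors to shrink by √(1000/180), rounded to 2.4, and concludes that the treatment-effect interval "will have width of approximately \$0.21 per item, or roughly 10% of the average estimated bias". The interval for the targeting covariance is put at 0.26 dollars squared.

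For older adults it plans 250 per label comparison (125 control, 125 label) and assumes the same variances as in the full sample. It then says "we will have standard errors that are $\sqrt{250/180} \approx 1.4$ times smaller than in our preliminary work". From this it derives a treatment-effect interval with "width of approximately \$0.36 per item, or roughly 20% of the average estimated bias for the full population", and a covariance interval that "will have width of approximately 0.45 dollars squared".

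Sections 4 and 5 of the Protocol set the share of adults aged 65 or older at about 25% of the beverage sample.

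**The concern.** The number printed after the square root is the ratio before the root is taken. If the unrooted ratio was also used to scale the pilot widths, both older-adult widths are too narrow, and the error runs in the favourable direction.

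This matters because interval width is the SAP's only argument that the sample is large enough, and this paragraph is its only statement of precision for a group that the Protocol deliberately over-recruits. The covariance width deserves particular attention. The covariance of treatment effect and bias enters the welfare formula directly (SAP, Proposition 1), and the pilot estimate was close to zero (SAP, Related Preliminary Work). How small a covariance the older-adult sample can separate from zero depends on the half-width of that interval.

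**Working it through.** **Inputs** (SAP, Sample Size and Power, unless noted)
- Pilot: 180 per label comparison; treatment-effect width $0.50.
- Full sample: 1,000 per comparison; stated factor 2.4; stated widths $0.21 and 0.26 dollars squared.
- Older adults: 250 per comparison; same variances; stated factor 1.4; stated widths $0.36 and 0.45 dollars squared.
- Mean estimated bias: $1.95 (SAP, Estimating bias).

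**Formula.** With equal variances and 1:1 arms, interval width is proportional to 1/√n, so new width = pilot width / √(n_new / n_pilot).

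**1. Reproduce the full-sample line.** √(1000/180) = √5.556 = 2.357, and 0.50/2.357 = $0.212. The SAP's 2.4 and $0.21 follow, so the root was applied here.

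**2. Apply the same formula to older adults.** 250/180 = 1.389 and √1.389 = 1.179.
- Treatment effect: 0.50/1.179 = $0.424, which is 0.424/1.95 = 21.8% of the mean bias. The stated $0.36 is 0.36/1.95 = 18.5%.
- Covariance: the pilot width is not stated. Working back from the full sample it is 0.26 × 2.357 = 0.613, or 0.26 × 2.4 = 0.624. Dividing by 1.179 gives 0.520 to 0.529 dollars squared.

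**3. Find where the stated figures come from.** Without the root, the factor is 1.389, which rounds to 1.4. Then 0.50/1.389 = $0.360 and 0.624/1.389 = 0.449, which rounds to 0.45. All three printed figures come back.

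Other readings do not return all three:
- t instead of normal quantiles: $0.423.
- 125 older adults on a label against all 500 controls: factor √[(2/90)/(1/125 + 1/500)] = 1.49.
- 375 per comparison: factor 1.44, widths $0.346 and 0.425.

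**4. Check within the section.** 250 is exactly a quarter of 1,000. Under equal variances the older-adult widths must be √4 = 2 times the full-sample widths: 2 × 0.21 = $0.42 and 2 × 0.26 = 0.52 dollars squared. This needs neither the pilot widths nor any figure from outside the section.

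**5. Rule out rounding of the pilot width.** A correct $0.36 would require a pilot width of 0.36 × 1.179 = $0.424. The full-sample width would then be 0.424/2.357 = $0.18, which contradicts the stated $0.21.

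**6. Size of the discrepancy.**
- Treatment effect: 0.424/0.36 = 1.18, so 18% wider (17% from the rounded $0.42).
- Covariance: 0.52/0.45 = 1.16 to 0.53/0.45 = 1.18, so 16 to 18% wider. The half-width is about 0.26 where the SAP implies 0.225.
- Older adults per comparison needed for $0.36: 180 × (0.50/0.36)² = 347, against 250 stated (39% more).

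**The case against.** The arithmetic has no defence; the case on the other side concerns how much it matters.

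**Little depends on it.** The SAP tests no hypothesis. No error rate, stopping rule, estimator or formal precision target uses 1.4, $0.36 or 0.45, and the final intervals will be computed from the trial data. This stands: no result can be biased by this line.

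**The summary phrase survives.** The SAP describes the treatment-effect width as roughly 20% of the average bias. The stated figure is about 18% and the corrected one about 22%, so the phrase holds loosely either way. This also stands, but it does not rescue the dollar figure, and the covariance width carries no such phrase.

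**The arm count is unsettled.** 500 per arm from 3,000 implies six arms, which fits the five labels mentioned under Related Preliminary Work. The Protocol (sections 1 and 4) describes three labels plus control. With equal allocation over four arms, 3,000 subjects and 25% aged 65 or older, a comparison would hold 2 × 3000 × 0.25/4 = 375 older adults, and the widths would be about $0.35 and 0.42 dollars squared, slightly better than printed. This is a fair reason to make the corrected widths conditional on 250 per comparison. It does not defend the text. The SAP states 125 + 125, and √(250/180) is 1.18 whatever the number of arms. With four arms the full-sample comparison would also grow, to 1,500, giving 0.50/√(1500/180) = $0.173, and the older-adult width would still be twice that. In addition, 3,000 is the Protocol's maximum and includes drop-outs, so the number analysed may be lower.

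**Conclusion.** The point holds. The SAP writes a square root but carries the unrooted ratio into the factor and both widths, while its full-sample line applies the root correctly. The two sets of figures cannot both follow from the stated assumptions.

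On the SAP's own terms (250 older adults per comparison, 1:1 arms, full-sample variances, pilot width of about $0.50), the factor is about 1.2, the treatment-effect width about $0.42 and the covariance width about 0.52 dollars squared. The covariance figure rests on doubling the rounded 0.26, and allowing for rounding it lies between 0.51 and 0.53. The design therefore delivers intervals about 16 to 18% wider than claimed for this subgroup. The practical effect is modest, but the statement is wrong as written and it is the SAP's only precision claim for older adults.

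**What to change.** In the older-adult paragraph of Sample Size and Power:
- Restate the factor as √(250/180) ≈ 1.2.
- Restate the treatment-effect interval width as about $0.42 per item, about 22% of the average estimated bias.
- Restate the covariance interval width as about 0.52 dollars squared.
- Say that these widths assume 250 per comparison. Recompute them, together with the full-sample widths, once the number of arms has been reconciled between the SAP and the Protocol.

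It would also help to print the pilot covariance width, so that a reader can check both covariance figures directly.

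The cost is SAP wording and slightly less favourable figures. Design, data collection and analysis do not change. If the investigators want to keep a width of $0.36, they need about 347 older adults per comparison, which would be a change to recruitment or allocation and not an edit.
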